#### **7.4. *End-of-Study Definition***

A subject enrolled in INTERRUPT AF is considered to have completed the study if he or she has completed all phases of the study including the last visit or the last applicable procedure shown in the Data Collection Schedule (table 8.1-1).

### **8. Study Methods**

#### **8.1. *Data Collection***

The data collection schedule is shown in Table 5.

**Table 5: Data Collection Schedule**

Data Collected	ENROLLMENT/ BASELINE		INDEX PROCEDURE (Day 0)	PRE-DISCHARGE (0-7 days post -procedure)	1-MONTH FOLLOW-UP (30±7 days)	3-MONTH FOLLOW-UP (90±30 days)	6-MONTH FOLLOW-UP (180±30 days)	12-MONTH FOLLOW-UP (365± 30 days)	24 MONTH FOLLOW-UP (730 ± 30 days)	36 MONTH FOLLOW-UP (1095 ± 30 days)	ADDITIONAL FOLLOW-UP	REPEAT PROCEDURE
Informed Consent	X											
Inclusion/Exclusion	X											
Demographic data	X											
Medical History	X											
Vitals	X		X		X			X	X	X	X	
Pre-Procedure Assessment	X											
Imaging	X a		X a		X a		X a			X a	X b	
Medication Regimen	X	X	X	X	X	X	X	X	X	X	X	X
Procedure data		X										X
EQ-5D	X				X	X	X					
AFEQT	X				X	X	X					
12-Lead EKG	X		X		X		X	X	X	X	X	
Event Monitor					X	X	X				X c	
Holter Monitor							X			X		
Documentation of Intervention for AF/AT/AFL				X	X	X	X	X	X	X	X	
Protocol Deviations	X	X	X	X	X	X	X	X	X	X	X	X
Adverse Event/Device Deficiency Reporting	X	X	X	X	X	X	X	X	X	X	X	X

a: If Pulmonary Vein Stenosis suspected or per center standard of care

b: Required for repeat procedures with non-study catheters only

c: If completed before the 12-month follow-up visit

### **8.2. Study Candidate Screening**

Investigators are responsible for screening all subjects and selecting those who are appropriate for study inclusion. The subjects selected for participation should be from the investigator's general patient population. The investigator is expected to follow standard of care testing to diagnose and screen subjects for inclusion in the study.

### **8.3. Informed Consent**

Patients who meet all of the inclusion criteria and none of the exclusion criteria and agree to participate in the INTERRUPT AF study must provide written informed consent approved by the regional regulatory body and the investigational center's IRB/EC prior to study participation and study specific testing or data collection.

The subject should be given ample time to consider participation and ask questions if necessary. An approved informed consent form (ICF) shall be signed and personally dated by the subject (or legal representative). The original, signed document is to be kept with the subject's file and a copy of the signed ICF must be provided to the subject. The index procedure must be performed within 60 days post ICF signature. In case the index procedure has not been performed within this time period, the subject may not be reconsented and will be classified as an INTENT (see section 8.3).

For additional information regarding the informed consent process, refer to Section 19.

### **8.4. Enrollment/Baseline Visit**

Subjects who provide written consent and meet all of the study enrollment criteria are enrolled in the study.

Enrolled subjects will have baseline data collected. The data collection at baseline includes:

- Visit date;
- Demographic data, including: age at time of consent, gender, race and ethnicity;
- Vitals including: height, weight, resting heart rate, systolic and diastolic blood pressure;
- Medical history, including:
  - Underlying cardiovascular disease, if any;
  - Prior history of cardiac events including: acute myocardial infarction, CVA, TIA, PE or transient ischemic attack;
  - Prior surgical interventions and/or cardiac procedures including: PTCA, CABG, pacemaker implantation, ICD implant, CRT implant, cardiac valve interventions, left atrial appendage closure, patent foramen ovale intervention, heart transplant or procedures for implantation of other intracardiac devices;
  - Detailed history of all arrhythmias and previous cardiac ablation procedures (catheter delivered or surgically performed), if any, including date of latest ablation procedure and any concomitant procedures (e.g., valve surgery, left atrial appendage closure or ligation, etc.), treated arrhythmia(s) and outcome;
  - Non-cardiac comorbidities.

- Pre-procedure assessment of Left Ventricular Ejection Fraction, Left Ventricular Diastolic Diameter, and Left Atrial Diameter within the past six months including data collection methods (if available)
- Current cardiovascular medication regimen including anti arrhythmic, anticoagulation and antiplatelet agents.
- Imaging
- 12-Lead EKG data including ongoing rhythm
- Quality of Life Instruments (AFEQT and EQ-5D-5L)

Evidence of PAF in the medical history should be documented and reported in the CRFs including date of last recorded episode, source of recording (Holter, EKG, etc) and treatment history (drug, cardioversion, etc).

#### **8.4.1. Medications**

#### **8.4.2. Anti-Arrhythmic Drugs**

It is recommended that all Anti-Arrhythmic Drugs (AADs) should be stopped at least five half-lives before the procedure; amiodarone should be stopped one month before the procedure.

It is recommended that AADs only be prescribed after the procedure if a subject has a documented arrhythmia recurrence. Post-procedure AADs are allowed per physician's discretion but new AADs should not be prescribed unless considered medically necessary. At eight weeks, investigators should remove subjects from AADs to appropriately assess the subject for early arrhythmia recurrence that may require a repeat ablation procedure within the blanking period (on or before day 90)

If the investigator determines that the subject must remain on an AAD after the blanking period, the subject will be considered a Primary Effectiveness Failure.

Treatment with Class II/IV medications for conditions other than control of arrhythmia recurrence is also permitted and will be documented. Every effort should be made to keep those drugs at a stable dose over the entire course of the study.

#### **8.4.3. Anticoagulation**

It is expected that the patient population for the study will have differing anticoagulation therapies. The requirements outlined below represent the minimum requirement of the study. Additional screening/testing is allowed if deemed necessary by the investigator.

The following subject groups should get a trans-esophageal echocardiogram (TEE) or equivalent to confirm absence of thrombus in the left atrium within 48 hours prior to the ablation:

- Patient presenting in Atrial Fibrillation at the time of the index procedure
- Patients presenting in Sinus Rhythm but with unknown anticoagulation pre-procedure

- Patient presenting in Atrial Fibrillation that have not been therapeutically anticoagulated for three weeks
- Patients with known cardiac thrombus within the past 90 days

It is also recommended that the following groups get a trans-esophageal echocardiogram (TEE) or equivalent to confirm absence of thrombus in the left atrium within 48 hours prior to the ablation:

- Patient presenting in Atrial Fibrillation and that have been therapeutically anticoagulated for three weeks
- Patient presenting in Sinus Rhythm that have not been therapeutically anticoagulated for three weeks

Confirming the absence of thrombus is not required for subjects in sinus rhythm that have therapeutic anticoagulation for three weeks.

Administration of anticoagulation on the morning of the index procedure is optional and investigators are encouraged to follow their standard of care. Per the Instructions For Use of the study devices, the activated coagulation/clotting time (ACT) level must be brought to a level  $\geq 300$  seconds and be checked at clinically appropriate intervals per center's SOC. No ablation can be performed until a minimum ACT of 300 seconds is obtained.

After the index procedure, all subjects will be required to be anticoagulated, using the drug determined best for the subject by the investigator, for a minimum of 60 days. All anticoagulation medications and INR levels, if applicable, will be collected throughout the course of the study.

### **8.5. *Ablation (index) procedure***

The index procedure for the INTERRUPT AF Study will consist of de novo PAF procedures. For the purposes of this protocol, de novo procedures are defined as AF procedures in which there has been no prior ablation in the Left Atrium (LA).

Esophageal temperature monitoring is highly recommended and should be performed per the center's standard of care. Esophageal temperature should be monitored and ablation delivery should be guided by rapid temperature rise or when temperature reaches a predefined threshold per standard of care.

The objective of the procedure is map-based electrical isolation of all pulmonary veins. Physicians will follow their preferred ablation workflow utilizing a Boston Scientific Open-Irrigated Catheter following all applicable Instructions for Use.

Once isolation of PVs has been attempted, the investigator may check for gaps with a validation map (vMap). This may be done on a per vein, per side, or whole chamber basis according the investigator's discretion. vMaps must be created while the subject is in sinus rhythm or during pacing. Adenosine or isoproterenol testing may be performed per center's standard of care and will be noted in the CRF.

Final confirmation of entrance block must be by vMap made at least 20 minutes after the last ablation (for that PV). Exit block verification is also highly recommended and will be noted in the CRF if completed.

Electrical isolation of the veins must be demonstrated by the absence of electrical propagation within the ablation lines.

Additional ablations may be performed according to medical judgement and clinical practice. If gaps are present, additional RF applications can be applied as required. Ablation of Induced Arrhythmias is allowed during the procedure as well as any previously documented arrhythmias. All additional ablations will be noted on the CRF.

Mapping/Ablation data collected during the procedure will include but may not be limited to:

Data Requirements	
Catheter model(s) and lot/serial number(s) used	
Presenting Rhythm	
Esophageal Temperature Monitoring (if applicable)	
Programmed ablation catheter fluid infusion rates	
Location of all previous ablations in any chamber (RF, Cryo, Surgical)	
Primary ablation targets	
Location of and reason for additional ablations performed beyond PVI	
Detection of gaps in ablation lines of index procedure (including locations)	
Number of ablation attempts (See Table 11 for definition) needed to close gap in ablation line/per gap for index procedure	
Did PV isolation terminate AF?	
What rhythm did AF terminate to?	
Adenosine testing result (if performed)	
Isoproterenol testing information (if performed)	
Was isolation achieved for each PV at the end of the procedure? (Documented via electrogram printouts)	
Name of map(s) that demonstrates PVI	
Acute success verification technique	
Was exit block tested? If, so was exit block achieved?	
Total Procedure Time (first catheter inserted to last catheter removed)	
Total Fluoroscopy Time	
Total RF time for the procedure	
Total fluid infused from ablation catheter	
Total mapping time	
Number of maps created	
Mapping time for each map	
Reason for map creation (list for each map)	
Map Completeness	
Number of points in each map	
Specific use of Rhythmia features	
Rhythm at end of case	
Was Cardioversion performed during the procedure? If so, when?	
Electronic Map Data*	

\* At the conclusion of the procedure, the Electronic Map Data collected through the Rhythmia Mapping System will be saved and stored in anonymized form by the site or sponsor representative onto external media provided by the Sponsor. Media will be returned to the Sponsor at the end of the study or at periodic intervals during the study.

### ***8.6. Pre-Discharge Follow-up***

The pre-discharge follow-up visit should be completed before the subject is discharged from the hospital. The visit should occur within seven days post-index procedure. If the subject is to remain in the hospital beyond seven days post-index procedure, then the pre-discharge follow-up visit should be conducted before the eighth day.

The data collection at Pre-Discharge includes:

- Date of visit;
- Vitals including: height, weight, resting heart rate, systolic and diastolic blood pressure
- Rhythm at time of visit (12-Lead EKG);
- Variations in current medication regimen
- Imaging (collected only if performed, if PV Stenosis suspected or according to center's practice)
- Reportable Adverse Events, if applicable
- Protocol Deviations, if applicable

### ***8.7. One-Month Follow-up (Phone Check)***

The one-month follow-up should be completed between 23 and 37 days post-procedure. The one-month follow-up can be performed over the phone or in clinic according to the site's standard practice.

The data collection at the one-month follow-up includes:

- Date of visit
- Review of any symptomatic transmissions (event monitor)
- Variations in current medication regimen
- Documentation of any intervention for AF/AT/AFL (e.g.: Repeat Procedure, Cardioversion), if applicable
- Reportable Adverse Events, if applicable
- Protocol Deviations, if applicable

### ***8.8. Three-Month Follow-up***

The three-month follow-up visit should be completed between 60 and 120 days post-procedure. Due to the range for the visit completion and the endpoint requirement for medication, AAD medication changes made during the three-month follow-up visit will be counted as being made within the blanking period, but efforts should be made to remove subjects from AADs by eight weeks post-procedure to allow for complete washout.

The data collection at the three-month follow-up visit includes:

- Date of visit
- Vitals including: height, weight, resting heart rate, systolic and diastolic blood pressure
- Rhythm at time of visit (12-Lead EKG)
- Review of any available symptomatic or asymptomatic transmissions (event monitor)
- Variations in current medication regimen
- Imaging (collected only if performed, if PV Stenosis suspected or according to center's practice)
- Quality of Life Instruments (AFEQT and EQ-5D-5L)
- Documentation of any intervention for AF/AT/AFL (e.g.: Repeat Procedure, Cardioversion), if applicable
- Reportable Adverse Events, if applicable
- Protocol Deviations, if applicable

#### ***8.9. Six-Month Follow-up (Phone Check)***

The six-month follow-up should be completed between 150 and 210 days post-procedure. The six-month follow-up can be performed over the phone or in clinic according to the site's standard practice.

The data collection at the six-month follow-up includes:

- Date of visit
- Review of any symptomatic or asymptomatic transmissions (event monitor)
- Variations in current medication regimen
- Imaging (collected only if performed, if PV Stenosis suspected or according to center's practice)
- Quality of Life Instruments (AFEQT and EQ-5D-5L)
- Documentation of any intervention for AF/AT/AFL (e.g.: Repeat Procedure, Cardioversion), if applicable
- Reportable Adverse Events, if applicable
- Protocol Deviations, if applicable

#### ***8.10. 12-Month Follow-up***

The 12-month follow-up visit should be completed between 335 and 395 days post-procedure.

The data collection at the 12-month follow-up visit includes:

- Date of visit
- Vitals including: height, weight, resting heart rate, systolic and diastolic blood pressure
- Rhythm at time of visit (12-Lead EKG);

- Review of any symptomatic or asymptomatic transmissions (event monitor);
- Collection and Review of 24-hour Holter Monitor for symptomatic or asymptomatic events
- Variations in current medication regimen;
- Imaging (collected only if performed, if PV Stenosis suspected or according to center's practice)
- Quality of Life Instruments (AFEQT and EQ-5D-5L)
- Documentation of any intervention for AF/AT/AFL (e.g.: Repeat Procedure, Cardioversion), if applicable
- Reportable Adverse Events, if applicable
- Protocol Deviations, if applicable

### ***8.11. 24-Month Follow-up***

The 24-month follow-up visit should be completed between 700 and 760 days post-procedure.

The data collection at the 24-month follow-up visit includes:

- Date of visit
- Vitals including: height, weight, resting heart rate, systolic and diastolic blood pressure
- Rhythm at time of visit (12-Lead EKG)
- Variations in current medication regimen
- Documentation of any intervention for AF/AT/AFL (e.g.: Repeat Procedure, Cardioversion), if applicable
- Reportable Adverse Events, if applicable
- Protocol Deviations, if applicable

### ***8.12. 36 Month Follow-up***

36-month follow-up visit should be completed between 1065 and 1125 days post-procedure.

The data collection at the 36-month follow-up visit includes:

- Date of visit
- Vitals including: height, weight, resting heart rate, systolic and diastolic blood pressure
- Rhythm at time of visit (12-Lead EKG)
- Collection and Review of 24-hour Holter Monitor for symptomatic or asymptomatic events
- Variations in current medication regimen
- Documentation of any intervention for AF/AT/AFL (e.g.: Repeat Procedure, Cardioversion), if applicable
- Reportable Adverse Events, if applicable
- Protocol Deviations, if applicable

### ***8.13. Additional Follow-up Visits***

An Additional follow-up visit is any subject visit triggered by subject symptoms that is not already defined as one of the study visits.

If subjects experience symptoms associated with cardiac arrhythmias (e.g. palpitations, lightheadedness, syncope, dyspnea) during the first 12 months, they will be instructed to record the arrhythmia on the event monitor. The investigator will review the information transmitted and will contact the subject to schedule an additional office visit if necessary.

In addition to determining the best course of action for the subject (repeat ablation, medication adjustment), during the visit, the following will be collected:

- Date
- Vitals including: height, weight, resting heart rate, systolic and diastolic blood pressure
- Rhythm at time of visit (12-Lead EKG)
- Variations in current medication regimen
- Imaging (collected only if performed, if PV Stenosis suspected or according to center's practice)
- If performed before the 12-month visit, review of symptomatic episode event monitor transmissions by the subject since the last follow-up
- Any intervention for AF/AT/AFL (e.g.: Repeat Procedure, Cardioversion)
- Reportable Adverse Events, if applicable
- Protocol Deviations, if applicable

### ***8.14. Repeat Ablation Procedure***

It is known that a repeat ablation procedure may be necessary in certain subjects after the index ablation procedure due to recurrences of PAF or other tachyarrhythmias requiring treatment. One repeat procedure is allowed within the blanking period if considered medically necessary due to subject's intolerance of the arrhythmia. Data collection requirements for the repeat procedure are the same as those for the index procedure.

If an investigator believes it is in the subject's best interest to perform the ablation with a non-study catheter, the investigator may choose to withdraw the subject from the study prior to performing the procedure. Prior to study withdrawal and undergoing the repeat procedure with a different (non-study) catheter, imaging of the PVs is required. The appropriate type of imaging performed may be determined by the investigator. As available, the PV images must be reviewed against the pre-ablation imaging from the index procedure to rule out PV stenosis from the index ablation procedure. In addition, repeat ablation with a non-study catheter must occur  $\geq 30$  days after the previous ablation procedure.

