#### 9.1.2.3. Statistical Methods

For the primary effectiveness endpoint, the Kaplan-Meier 12 month (365-day) primary effectiveness event-free rate will be calculated. Subjects who withdraw from the study prior to 12 months without experiencing an event will be censored on the date of withdrawal. The 95% one-sided lower confidence limit of the observed primary effectiveness event-free rate will be compared to the performance goal of 50%. If the lower confidence limit is greater than the performance goal, the null hypothesis will be rejected. The lower confidence limit will be calculated as the pointwise confidence limit using the log-log methodology.

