#### 9.1.4. Tertiary Endpoint

##### **Chronic Effectiveness:** Evaluation of chronic recurrence at 24 months and 36 months

- Recurrence defined as intervention for atrial fibrillation, or new onset of atrial flutter or atrial tachycardia (repeat procedures, use of AADs, cardioversion), excluding repeat procedures during the blanking period.
- Data collection to include the diagnostic modality used to identify recurrence and the therapeutic intervention
- Chronic effectiveness will be evaluated using Kaplan-Meier methodology. The Kaplan-Meier 24 month and 36 month chronic recurrence-free rate will be calculated and presented along with the 95% confidence interval, calculated as the pointwise confidence limit using the log-log methodology. Subjects who withdraw from the study prior to the specified time point without experiencing an event will be censored on the date of withdrawal.

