2 PURPOSE OF STATISTICAL ANALYSIS PLAN

The statistical analysis plan described in this document is to provide endpoint related analysis details to supplement the statistical methods provided in the INTERRUPT AF protocol.

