3.2 Primary Effectiveness Endpoint

The primary effectiveness endpoint will be evaluated by the primary effectiveness event-free rate at 12 months post-procedure.

Primary effectiveness events will be defined as the following:

- Acute procedural failure
- More than one repeat procedure during the blanking period (90 days post index procedure)
- Documented atrial fibrillation, or new onset of atrial flutter or atrial tachycardia event (≥ 30 seconds in duration from an event monitor or Holter Monitor, or from a 10 second 12-lead EKG) between 91 days and 365 days post index procedure
- Any of the following interventions for atrial fibrillation, or new onset of atrial flutter or atrial tachycardia between 91 days and 365 days post index procedure:
 - Repeat procedure
 - Cardioversion
 - Prescribed any AAD*

*AADs for endpoint will consist of all Class I/III and any Class II/IV medications taken for control of AF/AT/AFL recurrence

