3.2.3 Statistical Methods

For the primary effectiveness endpoint, the Kaplan-Meier 12 month (365-day) primary effectiveness event-free rate will be calculated. Subjects who die or withdraw from the study prior to 12 months without experiencing an endpoint event will be censored on the date of death or the date of withdrawal. The 95% one-sided lower confidence limit of the observed primary effectiveness event-free rate will be compared to the performance goal of 50%. If the lower confidence limit is greater than the performance goal, the null hypothesis will be rejected. The lower confidence limit will be calculated as the pointwise confidence limit using the log-log methodology.

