3.3.3 Statistical Methods

For the secondary effectiveness endpoint, the Kaplan-Meier 12 month (365-day) secondary effectiveness event-free rate will be calculated. Subjects who die or withdraw from the study prior to 12 months without experiencing an event will be censored on the date of death or the date of withdrawal. The 95% one-sided lower confidence limit of the observed secondary effectiveness event-free rate will be compared to the performance goal of 50%. If the lower confidence limit is greater than the performance goal, the null hypothesis will be rejected. The lower confidence limit will be calculated as the pointwise confidence limit using the log-log methodology.

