3.4 Tertiary endpoint

Chronic Effectiveness: Evaluation of chronic recurrence at 24 months and 36 months

- Recurrence is defined as intervention for atrial fibrillation, or new onset of atrial flutter or atrial tachycardia (repeat procedures, use of AADs, cardioversion), excluding repeat procedures during the 90-day blanking period.
- Data collection to include the diagnostic modality used to identify recurrence and the therapeutic intervention
- Chronic effectiveness will be evaluated using Kaplan-Meier methodology. The Kaplan-Meier 24 month and 36 month chronic recurrence-free rate will be calculated and presented along with the 95% confidence interval, calculated as the pointwise confidence limit using the log-log methodology. Subjects who die or withdraw from the study prior to the specified time point without experiencing an event will be censored on the date of death or on the date of withdrawal.

Center Experience: Primary safety and Primary effectiveness outcomes by center experience

- In order to evaluate training effectiveness for investigators outside of the ZERO AF IDE study, outcomes in centers performing five or more procedures using the Blazer OI catheter during the ZERO AF IDE study will be compared to all other. Kaplan-Meier rates and 95% confidence intervals for the Primary Safety and Effectiveness endpoints for both groups will be presented with no statistical comparison.

Safety: Reportable Adverse Events rates at 12, 24 and 36 months

Adverse events will be collected at all subject follow-up visits. Reportable events include:

- All Serious Adverse Events
- All Study Procedure-Related Adverse Events
- All Study Device-Related Adverse Events
- All Study Device Deficiencies
- Unanticipated Adverse Device Effects/Unanticipated Serious Adverse Device Effects previously not defined in the Directions For Use.

Adverse event rates will be calculated using binomial methodology. The cumulative number of events and event rate will be included in all study reports. Subjects at risk for an adverse event will be determined by the subject treatment status; all treatment and attempt subjects will be considered at risk for study related adverse events

Effectiveness: Acute Procedural Success Rate

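### A subject withdrawn after day 90 for a planned repeat ablation with a non-study catheter is censored, although the same repeat is an effectiveness event if the subject stays in the study

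*Protocol*

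**What the plan says.** **Withdrawal route.** For a repeat ablation with a non-study catheter, protocol 8.14 says that "the investigator may choose to withdraw the subject from the study prior to performing the procedure". This is an option, not a requirement. Under protocol 7.2 no further data are collected after withdrawal. Permission to follow the subject is sought only when the withdrawal is due to device safety or performance.

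**Event definition.** SAP 3.2 counts a repeat procedure among the "interventions for atrial fibrillation, or new onset of atrial flutter or atrial tachycardia between 91 days and 365 days post index procedure". Protocol 4.2, 4.3, 9.1.2 and 9.1.3 and SAP 3.3 have the same element, and none limits it to study catheters. For the 24- and 36-month endpoint, recurrence means an intervention, and only repeat procedures in blanking are left out.

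**Censoring.**
- SAP 3.2.3, primary, using the day on which the subject died or withdrew: "Subjects who die or withdraw from the study prior to 12 months without experiencing an endpoint event will be censored on the date".
- SAP 3.3.3, secondary, using the same day: "Subjects who die or withdraw from the study prior to 12 months without experiencing an event will be censored on the date".
- SAP 3.4, 24 and 36 months: "Subjects who die or withdraw from the study prior to the specified time point without experiencing an event will be censored".
- Protocol 9.1.2.3 (and 9.1.3.3): "Subjects who withdraw from the study prior to 12 months without experiencing an event will be censored on the date of withdrawal".
- Protocol 9.1.4 (and 4.4 and the synopsis, tertiary endpoint): "Subjects who withdraw from the study prior to the specified time point without experiencing an event will be censored on the date of withdrawal".

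None of these makes an exception for the reason for withdrawal. The failure definitions in protocol Table 11 do not mention withdrawals under 8.14 either.

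**The concern.** Kaplan-Meier estimation assumes that a censored subject has the same later risk as those who remain. Subjects who leave under 8.14 do so because a repeat ablation is planned, and that repeat would itself be an event. For a subject with no earlier countable event, an optional administrative step thus decides whether the same outcome lowers the event-free rate or drops out of it.

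The plan already treats one comparable decision as failure: under protocol 8.4.2, a subject whom the investigator must keep on an AAD after blanking is a primary effectiveness failure. A decision to ablate again has no matching rule.

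At stake are the 12-month effectiveness estimates, the comparison with the 50% goal if the true rate lies near it, and the descriptive 24- and 36-month rates.

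**Working it through.** **1. The two paths for one planned repeat after day 90, no earlier event**

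| | Stays in study | Withdrawn first under 8.14 |
|---|---|---|
| Repeat recorded? | Yes | No (protocol 7.2) |
| 12-month endpoints, days 91-365 | Event | Censored |
| 24/36-month endpoint | Event | Censored |

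**2. The plan's own figure.** Inputs from SAP 3.2.2: 50% against 60%, one-sided 5%, 80% power, 7.5% attrition. An exact binomial calculation, taking the smallest n from which power stays at 80% or more, gives 169, and 169/0.925 = 182.7, that is 183 as stated. The same rule gives 304/0.925 = 328.6 (329, safety) and 76/0.925 = 82.2 (83, secondary). The sample sizes are not in dispute.

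**3. Size of the error.** Assumed inputs, not in the documents:
- s: share of all subjects withdrawn this way with no earlier event
- c: fraction of those planned repeats that are cancelled or fall after day 365
- a = 5% acute failures on day 0, with other failures uniform on days 91-365

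With true rate p and L = 1 - p - a:

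KM if censored = (1 - a) x [(p - s·c)/(1 - a)]^[(L - s(1 - c))/(L + s·c)]

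KM if counted as events = p - s·c

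For p = 0.60, s = 0.02, c = 0: 0.95 x (0.60/0.95)^(0.33/0.35) = 0.616, or +1.6 points. At s = 0.01 the exponent is 0.34/0.35 and the result 0.608 (+0.8). At s = 0.005 it is 0.604 (+0.4).

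For p = 0.60, s = 0.02 with some repeats not done by day 365:

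| c | Censored | Counted as events |
|---|---|---|
| 0% | +1.6 | 0 |
| 25% | +1.1 | -0.5 |
| 50% | +0.6 | -1.0 |

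Over p = 50-65% and a = 2-10%, the two rules are equally far off at c = 35-43%. Censoring is unbiased only at c = 70-85%.

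**4. Probability of passing.** Kaplan-Meier simulation, N = 329, 20,000 replicates, one-sided 95% log-log lower limit against 50%, independent attrition of 7.5% per year, every planned repeat done by day 365 (c = 0):

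| s | Subjects (329·s) | True 50% | True 55% | Planned 60% |
|---|---|---|---|---|
| 0% | 0 | 4.6% | 54.0% | 97.1% |
| 0.5% | 1.6 | 5.8% | 58.0% | 97.8% |
| 1% | 3.3 | about 7.6% | 63.8% | 98.5% |
| 2% | 6.6 | about 12% | 73.4% | 99.2% |

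Repeat runs moved the true-50% column by up to about half a point. That column is the worst case. With 25% and 50% of repeats not done it falls to about 6.4% and 5.4% at s = 1%, and to about 9% and 6-7% at s = 2%.

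**5. Other endpoints.** Secondary, at the planned 65%: +0.4, +0.8 and +1.7 points at s = 0.5, 1 and 2%, with a pass probability of 100% throughout. Tertiary, for an assumed true 36-month rate of 60-80%: s = 1% adds 0.5-0.6 points at 24 months and 0.8-0.9 at 36 months; s = 2% adds 1.1-1.2 and 1.6-1.9.

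**The case against.** **Few subjects can fall in the gap for the primary endpoint.** After day 90, documented AF or new-onset flutter or tachycardia already counts, as does an AAD prescribed for it. Subjects are asked for at least two monitor transmissions a month (protocol 10.4.1.1), and symptom-triggered visits include a 12-lead EKG (protocol 8.13). This stands, and it is why no share can be claimed. It protects the secondary endpoint less: AF must be symptomatic, which Table 11 ties to seeking care and a concurrent recording, and an unchanged baseline AAD does not count. It does not protect the 24/36-month endpoint, where only interventions count.

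**SAP 5.6.2 already turns withdrawals into events one by one.** It does, for the primary endpoint only, pooled with deaths and all other withdrawals. It changes neither the estimate nor the pass rule.

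**Counting a planned repeat treats an intention as an event.** True. This is closer to the truth only if roughly 65% or more of the planned repeats occur by day 365, which is unknown. The objection justifies using the planned date and keeping the present rule as a sensitivity analysis.

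**Stronger readings to avoid.** A reader might infer from the 12% figure that the trial's type I error is badly inflated. That figure needs an assumed 2% share, a true rate exactly at the goal and every repeat done in time. A reader might also infer that every 8.14 withdrawal hides a failure. Subjects with an earlier event are already counted, and a single repeat in blanking is not an event.

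**Conclusion.** The inconsistency is certain on the text: no rule separates a withdrawal under 8.14 from any other, and the repeat it precedes is an event for those who stay. The error favours the device unless about 70% or more of the planned repeats are cancelled or fall after day 365.

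Its size rests on an assumed share. The number affected is probably small for the primary endpoint, larger for the secondary and largest for the 24/36-month endpoint, which is descriptive and has no performance goal. At the planned 60% the cost is an estimate 0.4 to 1.6 points too high for shares of 0.5% to 2%, and the pass decision rarely changes. It becomes sensitive only if the true rate is near 50%.

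This should be fixed before the 12-month analysis, because the repair is cheap. Confidence is medium: the text is clear, the frequency is not.

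**What to change.** 1. **Event rule.** State that a subject with no earlier event, withdrawn on days 91-365 with the recorded reason of a planned repeat ablation with a non-study catheter for AF or new-onset flutter or tachycardia (8.14), is an effectiveness event on the withdrawal date. If the planned procedure date recorded at withdrawal is after day 365, the subject is censored for the 12-month endpoints. At 24 and 36 months apply the same rule to withdrawals after day 90, with each time point's own cut-off.
   - Event definitions: synopsis (primary and secondary effectiveness), protocol 4.2, 4.3, 9.1.2, 9.1.3, both effectiveness-failure entries in Table 11, and SAP 3.2 and 3.3.
   - Censoring sentences: SAP 3.2.3, 3.3.3 and 3.4; protocol 9.1.2.3, 9.1.3.3, 9.1.4 and 4.4; synopsis (tertiary endpoint).
2. **Sensitivity analyses.** (a) The current censoring rule. (b) Withdrawals under 8.14 on or before day 90 with a planned procedure date after day 90 counted as events.
3. **Data.** On the End of Study eCRF, record at withdrawal the 8.14 reason, the target arrhythmia and the planned procedure date. This needs no data after withdrawal, so it fits protocol 7.2.
4. **Reporting.** Give the number of 8.14 withdrawals and how many had no earlier event.

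**Cost.** A protocol amendment as well as a SAP amendment, since the SAP's stated purpose is "to provide endpoint related analysis details to supplement the statistical methods provided in the INTERRUPT AF protocol", and up to three eCRF fields (the form is not in the documents and may already hold some). For subjects already withdrawn, the PV imaging that 8.14 requires can help to identify them. If all planned repeats would have taken place, the reported rate drops by 0.8 points at a 1% share and 1.6 at 2% (true 60%). Where some do not, the estimate is too low by s·c: 0.02 x 0.25 = 0.5 points. No change to the clinical rule in 8.14 is proposed.
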